3.6 Data analysis plan

Using descriptive statistics, we will present demographic and clinical baseline characteristics of our study population.

3.6.1 Primary analysis

We will report descriptive summary statistics of the performance of the study population at each of the 4 CBB tasks for each of the preoperative and postoperative time points. We will also represent individual and averaged performance trajectories graphically.

To explore whether surgery has a statistically significant impact on cognitive performance and its trajectories, we will model data using interrupted time series analyses. Interrupted time series analysis is a powerful quasi-experimental design to study the longitudinal effects of interventions or exposures, accounting for pre-intervention/pre-exposure trends. We will adopt the approach described in Kontopantelis *et al.*, *BMJ* 2015.^{21 22} According to this approach we will use regression models in which the within patient performance variation over time is partitioned into three main components, to provide independent tests for the slope in scores in the pre-operative period (test 1); the change in level (i.e., absolute change) around surgery, allowing for the trend before surgery (test 2); and the change in slope from before to after surgery (test 3).^{21 22} The preoperative slope quantifies the trend in performance before surgery. The level change is an estimate of the absolute change in cognitive performance that can be attributed to surgery, i.e., between the time points immediately before and immediately after surgery, and accounting for the preoperative trend. The change in slope quantifies the difference between the preoperative and postoperative slope. Based on the hypothesis that the postoperative trajectory will not be homogenous over the 12 months after surgery, we will also adopt a more complex interrupted time series model that will allow for different slopes of change in different time segments, i.e. right before to 1 month after surgery, 1-3 months, 3-6 months, and 6-12 months after surgery.²³ We will conduct the primary analysis first considering only the early-intermediate postoperative performance (up to 6 months after surgery). With the assumption that the

impact of surgery can last as long as one year,² we will repeat the analysis including also the change between 6 and 12 months after surgery. In our regression models, we will use estimates of error variance obtained from bootstrap techniques using 1000 bootstrap samples. We will analyze the performance at each task separately, and then combining the 4 scores into one unique measure of performance. We will explore whether clinically significant changes have occurred at any time point. There is no standard definition for what is a clinically significant perioperative decline across different tests.^{24 25} In addition to the change as defined in our sample size calculation (i.e. a change in score equal to or greater than the average difference in scores between a healthy older adult and a subject with MCI), we will consider also 2 most commonly adopted definitions, i.e. 1) a change of $\geq 20\%$ in test scores,²⁶ and 2) a reliable change index (RCI) of ≥ 1.65 . The RCI is an index commonly used in neuropsychology,²⁷ and also in studies using the CBB,¹³ calculated by dividing the individual's test-retest difference score by the standard error of that difference score, and can be interpreted as a standard Z score. The cut-off of RCI=1.65 is the point beyond which 5% of the values from the normal sample population will fall (i.e. $P<0.05$, one tailed test). We will compare the performance scores at each time point with the preceding time points, and evaluate the changes based upon these criteria. We will provide the number and percentage of patients experiencing a cognitive decline based on these definitions at each of the segments of the observation period. We will also compare our study population data with existing age-stratified normative data for the CBB.²⁸

In our primary analyses, we will include only patients who completed ≥ 2 assessments preoperatively and ≥ 3 assessments (i.e. 1, 3, and 6 months) postoperatively. Secondarily, we will repeat our analysis dealing with missing data 1) through multiple imputation techniques; and 2) using a method of evidence-informed data imputation, previously implemented in our studies, which takes onto account the reason for the missing data.³

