Based on industry web standards, the Cogstate system will communicate with the McMaster system through an Application Programming Interface (API), to generate user- and visit- specific links. The CBB will be host in a McMaster webpage, in a seamless fashion for the participant, who will be directed into the Cogstate application when they start the assessment, and then back to the hosting website upon completion of the tests. The CBB will present each cognitive test to the subject following a self-paced training test until valid cognitive data is provided, enabling testing without supervision. Subjects will receive a simple message at the end of their testing session indicating next steps. A detailed report with cognitive data will not be provided to subjects. For the purpose of this study, a support person will be allowed to attend the self-administration of the CBB. This will be established at the enrolment for each participant, and the participant will be instructed to self-administer the CBB under the same conditions at every assessment over time.

After 1-5 days from the initial recruitment and training session, each participant will self-administer the cognitive testing once, and then every month (i.e. 30 days, ± 1 week) until their surgery is performed. We expect that each participant will have at least 2 assessments before surgery. Participants will then self-administer the CBB 1 month, 3 months, 6 months, and 12 months after surgery.

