3.5 Sample size

The slowdown of the operating rooms due to COVID-19 started in mid-March, and it will last at least until the end of June or July at the participating sites. We expect to recruit 330 participants between May and August 2020. This sample size will be sufficient to test our primary hypothesis that, on average, in our population, the cognitive performance at 6 months after surgery will be worse, in a clinically significant way, compared to what we would expect based on the preoperative trajectory. We will base our primary hypothesis on the performance at the *One-Back Task (OBK)* of the CBB, at 6 months after surgery. The *OBK* assesses working memory, which is a cognitive domain often found altered in the context of postoperative cognitive dysfunction. It uses a well-validated n-back paradigm with stimuli from playing cards. The subject is asked whether the card displayed in the center of the screen is the same as the card presented immediately before. The subject responds by pressing the “yes” or “no” key. The primary outcome variable for this test is accuracy of correct response, normalized using an arcsine square-root transformation. In **APPENDIX II** we provide a table summarizing the clinical relevance of the test and its results, with data on the difference in performance between healthy older adults, and older adults with mild cognitive impairment (MCI) or dementia based on standardized neuropsychological assessment.^{13 19} Based on the literature, a typical score of healthy older adults is 1.35; the average difference, at one time point, in the *OBK* score, between healthy older adults and older adults with mild cognitive impairment (MCI), and older adults with dementia, is, respectively, 0.07 and 0.17.^{13 19} We hypothesize that in our study population we will see a preoperative trajectory, which, if it continued, unchanged, after surgery (H_0), would lead to an average decrease in OBK score of 0.009 over 6 months. This is still consistent with a decline over time compared with what we would expect on average in a healthy older population.^{13 19} Our hypothesis (H_1) is that surgery will change the preoperative trajectory so that at 6 months after surgery we will instead see an average decrease, compared with right before surgery, of 0.035 (which would correspond to the average change in a hypothetical population in which 40% of subjects experience a decline of at least 0.07, 50% no

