change, and 10% an improvement of 0.07). Based on a test of comparison of means in one sample, with an alpha error of 0.05 (2-tailed), and a standard deviation for the OBK score of 0.16,¹³ to enrol 330 subjects will be sufficient to test our hypothesis with 80% of power, even in case of an attrition rate as high as 10%.

Recruiting 330 participants is a feasible goal based on the current status of knowledge about the COVID-19 contingency plan. The lockdown of the operating rooms started in March and will last at least until the end of June, or longer, depending on the participating site. During the lockdown, we expect to be able to enroll at least 120 participants at McMaster sites, and 30-50 participants at each of the other participating sites. Even when the operating rooms will reopen to more elective surgeries in the next months, this will happen slowly, so that we expect a carryover of the lockdown at least until the end of the summer. Moreover, it is projected that, if countries increase their normal surgical volume by 20% post-pandemic, it would take a median 45 weeks to clear the backlog of operations resulting from COVID-19 disruption.²⁰ Therefore should we see a recruitment rate slower than expected, for any reason, we will extend our recruitment period to beyond the summer.

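### Section 3.6.1 does not name the OBK 6-month contrast sized in Section 3.5 as the deciding test; its listed tests are other quantities, and the 80% power does not carry over to that contrast

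*Combined protocol and SAP*

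**What the plan says.** Section 3.5 states a single primary hypothesis, that "the cognitive performance at 6 months after surgery will be worse, in a clinically significant way, compared to what we would expect" from the preoperative trajectory. It ties this to one task and one time: "We will base our primary hypothesis on the performance at the *One-Back Task (OBK)* of the CBB, at 6 months after surgery". Under the null the trajectory continues and OBK falls by 0.009 over 6 months; under the alternative it falls by 0.035. The sizing is "Based on a test of comparison of means in one sample, with an alpha error of 0.05 (2-tailed"), with SD 0.16 and 10% attrition, and concludes that "to enrol 330 subjects will be sufficient to test our hypothesis with 80% of power".

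Section 3.6.1 opens its modelling paragraph with "To explore whether surgery has a statistically significant impact on cognitive performance and its trajectories". Its regression partitions each patient's scores "to provide independent tests for the slope in scores in the pre-operative period (test 1); the change in level (i.e., absolute change) around surgery", and test 3 is the change in slope. The level change is defined between the points immediately before and after surgery. A second model with separate slopes by postoperative segment is added. The analysis runs first to 6 months and is then repeated to 12. On outcomes: "We will analyze the performance at each task separately, and then combining the 4 scores into one unique measure of performance".

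On preoperative data, Section 3.4.1 says "We expect that each participant will have at least 2 assessments before surgery", at monthly intervals. Section 1 describes preoperative follow-up of one to a few months. The primary analysis set in Section 3.6.1 requires at least 2 preoperative tests and the 1-, 3- and 6-month tests.

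**The concern.** In Section 3.6.1, six months appears as a data window, a segment boundary and a completeness rule, but not as the time of a named test, and OBK is not singled out. The only link back to the sample-size section is the definition of a clinically significant change. The status of the tests is also unclear, because one sentence speaks both of exploring and of statistical significance.

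Two things are at stake. First, a significant level or slope change, on OBK or another task, could be reported as the answer to the primary hypothesis although it answers a different question. The 0.05 error rate holds only if the OBK 6-month contrast alone decides. Second, once that contrast is named, the power in Section 3.5 no longer describes it. The one-sample formula treats the projected decline as a known constant, whereas the model estimates it from as few as 2 preoperative tests and projects it 6 months ahead.

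**Working it through.** **Inputs from the documents.** Effect 0.035 - 0.009 = 0.026; SD 0.16 (the single-time-point SD in healthy older adults in Appendix II); two-sided 0.05; 330 × 0.9 = 297 completers; monthly preoperative tests; postoperative tests at 1, 3 and 6 months.

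**Assumptions.** The documents give neither the within-patient correlation ρ nor the distribution of preoperative tests. I use ρ = 0.5-0.9 (random intercept), the last preoperative test 0-1 month before surgery, and 2, 3 or 4 tests or an equal mix of these.

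**1. The plan's figure.** n = (0.16 × (1.960 + 0.842) / 0.026)² = 298, and 298/0.9 = 332, close to 330. With 297 completers the SE is 0.16/√297 = 0.0093, z = 0.026/0.0093 = 2.80, and power is 80%. The arithmetic is sound for a mean tested against a known constant.

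**2. The hypothesis in model terms.** With time t in months from surgery and postoperative indicator P,

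E(Y) = b0 + b1·t + b2·P + b3·P·t.

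Test 1 concerns b1, test 2 b2 and test 3 b3. Observed minus projected at 6 months is b2 + 6·b3.

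**3. The listed tests can disagree with that contrast.**
- *Early drop, recovered at 6 months.* Take true deviations of -0.06, -0.03 and 0 at months 1, 3 and 6. The fitted postoperative line has slope change 0.15/12.667 = 0.0118 and level change -0.03 - 0.0118 × 3.333 = -0.0695, so the contrast is about 0.002. At ρ = 0.7 with the equal mix, test 2 has z = -7.8 to -9.7 and test 3 has z = 3.5 (1.6 if every patient has 2 tests), while the 6-month contrast has z below 0.1.
- *Steady decline to -0.026 at 6 months.* The level change is exactly 0.

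**4. Power of the 6-month contrast with the trend estimated.** In the piecewise model, with k preoperative tests at mean time m and sum of squares S, the per-patient variance is

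0.16² × (1 - ρ) × [1 + 1/k + (6 - m)²/S].

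Example with ρ = 0.7 and the last test 0.25 month before surgery:
- k = 2: m = -0.75, S = 0.5, bracket 92.6, per-patient SD 0.843, SE 0.843/√297 = 0.049, power 8%.
- k = 4: m = -1.75, S = 5, bracket 13.3, SD 0.319, SE 0.0185, power 29%.

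The segmented model agrees within 0.5 percentage point for 2 to 4 tests. Its power for a 0.026 deficit with 297 completers, each range covering a last test 0-1 month before surgery, is:

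| Preoperative tests | ρ = 0.5 | ρ = 0.7 | ρ = 0.9 |
|---|---|---|---|
| 2 | 7% | 8-9% | 13-16% |
| 3 | 11-12% | 14-17% | 34-42% |
| 4 | 17-20% | 25-31% | 61-71% |
| equal mix of 2, 3, 4 | 13-15% | 18-21% | 43-52% |
| 5 | 26-30% | 39-46% | 83-90% |
| 6 | 36-41% | 54-61% | 94-97% |

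With the equal mix, 80% power needs about 1,700-2,200 completers at ρ = 0.7, or 580-740 at ρ = 0.9. A patient-level random slope would lower power further.

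The loss comes from the projection and not from the SD. If the trend were known, the simple change would have SD 0.16 × √(2(1 - ρ)), which is 0.16 at ρ = 0.5 and 0.124 at ρ = 0.7, with power 80% and 95%.

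**5. False positives, only if several tests are read as confirmatory.** By simulation, at least one of tests 2 and 3 on OBK is significant under the null in 8-10% of trials. Over all five outcomes the figure is 24-37% (between-task correlation 0-0.5). The estimates behind tests 2 and 3 have correlation 0.05-0.76, so they are separate tests but not independent ones.

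**The case against.** Protocol and analysis plan are one document, and Section 3.5 already fixes task, time, comparator and alpha. Section 3.6.1 puts the 6-month window first, adds the piecewise model as a supplement and calls the 12-month run a repeat. The contrast can be recovered from the planned models. On this reading only a cross-reference is missing. That is a fair account of how small the repair is, but the text still does not say which result decides.

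The objectives are to describe and explore, so the false-positive rates describe a reading that the authors may not intend. This stands: those rates are conditional and carry little weight here. It does not remove the conflict, because Section 3.5 states a powered hypothesis.

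The illustrations are chosen to diverge. A gradual deficit is what test 3 targets, and the piecewise model anticipates a non-linear course. The examples show only that the quantities differ, which is the point being made.

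The power figures rest on assumed correlations and visit counts, and longer waits would help; Section 3.5 itself cites a projected median of 45 weeks to clear the surgical backlog. An equal mix of 2 to 6 tests would give about 77-86% at ρ = 0.9, but 35-42% at 0.7 and 23-27% at 0.5. So the loss is not inevitable, and no single figure above is the study's actual power. Against this, the plan relies on only 2 tests, and Section 1 expects one to a few months of preoperative follow-up. With 2 or 3 tests power is well below 80% at every correlation from 0.5 to 0.9.

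**Conclusion.** The concern holds. Section 3.6.1 does not designate the contrast that Section 3.5 sizes, and its three listed tests measure other quantities that can be strongly significant, or exactly zero, independently of the 6-month deficit. The 330 is correct arithmetic for a mean against a known value, but the 80% is not the power of the modelled contrast. With 2 to 4 preoperative tests and within-patient correlation 0.5-0.9, power runs from 7% to 71% (13-52% for an equal mix). It reaches 80% only with more preoperative tests, a very high correlation, or both. The exact figures depend on the assumed correlation, test timing and random-intercept structure. The conclusion that the projection error is omitted does not. This should be corrected before analysis; it does not affect data collection.

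**What to change.** In Section 3.6.1, name one primary test: the OBK contrast of observed minus projected score at 6 months, two-sided 0.05, reported with its confidence interval. State its source model: level change + 6 × slope change in the segmented model fitted to 6 months, or the equivalent 6-month deviation if the piecewise model is chosen. Label tests 1-3, the other three tasks, the composite, the other model and the 12-month repeat as secondary or exploratory. Describe the three tests as separate, not independent.

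In Section 3.5, restate the power for this contrast with an estimated preoperative trend. Give the assumed within-patient correlation and the expected distribution of preoperative tests, and show a range that includes 5-6 tests. If the restated power is not acceptable, present the contrast as an estimate with a confidence interval, in line with the descriptive and exploratory objectives, and drop the claim of a powered test.

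The cost is plan wording, one linear-combination command in Stata and a re-derived power statement. The drawback is that the other results become supportive, and the 80% is replaced by a figure that is likely to be clearly lower at 330 patients.

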1. BACKGROUND AND RATIONALE

The COVID-19 emergency has been impacting our patients and healthcare systems in several ways. To redeploy resources (staff and equipment) to priority areas, ensure hospital capacity to front the COVID-19 surge, and for infection control reasons, the use of operating rooms have been limited mainly to semi-urgent (e.g., oncology), urgent (e.g., hip fracture) and emergency (e.g., ruptured abdominal aortic aneurysm) surgeries, while many elective surgeries have been deferred to a later, often undermined, time. From a societal perspective, this is certainly thought to be the best choice in such an emergency. From an individual perspective this is going to represent a stressful situation for those patients, often older, whose surgery is not happening as planned.

On the other side, from an epidemiological perspective, this represents a unique opportunity to study the impact of surgery on cognitive performance. Postoperative cognitive dysfunction (POCD) is an objectively measured decline in cognition postoperatively compared with preoperative function.^{1,2} The NeuroVISION study demonstrated that as many as 30% of patients aged 65 or older undergoing elective noncardiac surgery experience cognitive decline at 1 year after surgery, defined as ≥ 2 point decline in the Montreal Cognitive Assessment compared with before surgery.³ This has questioned the role of surgery in cognitive decline. Many of these patients have several comorbidities, which, in addition to age, could theoretically impact their cognitive performance over time. Therefore, it is still uncertain whether the decline we see in these patients who underwent surgery is different from what we would have seen if the same patients had not undergone surgery. An epidemiological study could try to answer this question comparing the surgical cohort with a matched non-surgical cohort. However, whatever matching approach we use, the control group is always going to be imperfect, and undoubtedly inferior to an approach that compares the individual with themselves. However, when we evaluate the effect of surgery comparing the patient cognitive performance at a certain time point after surgery with the cognitive performance measured at only one time point before surgery, we miss considering a possible pre-existing trend over time before surgery, which could hypothetically explain the change after surgery.

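### The individual-decline rule fixes no preoperative reference and does not say how comparisons combine, so later-visit percentages can miss sustained decline or exceed the 5% attached to the RCI

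*Combined protocol and SAP*

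**What the plan says.** Section 3.6.1 gives three definitions of clinically significant individual change: a change at least as large as the difference between healthy older adults and those with mild cognitive impairment (0.07 on the One-Back Task), a change of at least 20%, and an RCI of at least 1.65. The RCI is "calculated by dividing the individual's test-retest difference score by the standard error of that difference score", and "The cut-off of RCI=1.65 is the point beyond which 5% of the values from the normal sample population will fall".

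The definitions are applied as follows: "We will compare the performance scores at each time point with the preceding time points, and evaluate the changes based upon these criteria". The output is "the number and percentage of patients experiencing a cognitive decline based on these definitions at each of the segments of the observation period". Earlier in the same section the postoperative segments are "right before to 1 month after surgery, 1-3 months, 3-6 months, and 6-12 months after surgery".

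Section 1 takes a different reference: "Postoperative cognitive dysfunction (POCD) is an objectively measured decline in cognition postoperatively compared with preoperative function". Section 3.5 also states the hypothesised 6-month change relative to the score just before surgery.

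**The concern.** The plan does not say which earlier score is the reference when a patient is called a decliner at a given visit, or how several comparisons become one classification. The concept in section 1 needs a preoperative reference. Reporting by segment points to a comparison with the previous visit.

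The choice changes what the later percentages mean. If month 6 is compared with month 3, a patient who fell by month 1 and never recovered shows no new change, and the 6-month figure says little about persistent decline from before surgery. If a patient is flagged against any earlier score, the share flagged by chance grows with the number of earlier tests. Under section 3.4.1 preoperative testing is monthly until surgery, so that number grows with the wait. In a study of deferred surgery, such a rise could be mistaken for an effect of deferral.

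**Working it through.** **Inputs from the documents.** RCI cut-off 1.65 with a one-tailed 5%; postoperative tests at 1, 3, 6 and 12 months; SD 0.16 and threshold 0.07 for the One-Back Task (section 3.5, Appendix II). For the primary analyses, "we will include only patients who completed ≥ 2 assessments preoperatively and ≥ 3 assessments" postoperatively. Month 6 therefore has at least 2 + 2 = 4 earlier tests.

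**Assumptions.** Normal, independent test errors with equal SD σ; no true change except where stated. The SE of a difference between two tests is σ√2. The test-retest correlation r is not given, so 0.5 to 0.9 is used, with σ = 0.16·√(1 − r).

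**1. The plan's own figure.** 1 − Φ(1.65) = 0.0495. The stated 5% is reproduced, for one pair of tests.

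**2. Segment-to-segment reading.** Let D be a fall in units of the SE of difference, present from month 1 and sustained.
- Month 1 against the last preoperative test: Φ(D − 1.65). For D = 2, Φ(0.35) = 64%.
- Month 3 against 1, 6 against 3, 12 against 6: the true difference is zero, so Φ(−1.65) = 4.9% for every D.
- Month 6 against the last preoperative test: 64% for D = 2, and Φ(1.35) = 91% for D = 3.
- Month 6 against the mean of two preoperative tests: the SE is σ√1.5, so detection is Φ(D·√(2/1.5) − 1.65). For D = 2, Φ(2.309 − 1.65) = 75%.

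**3. The same contrast for a sustained fall of 0.07.** Against the mean of two preoperative tests, detection is Φ(0.07/(σ√1.5) − 1.65).

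| r | σ | 0.07/(σ√1.5) | Flagged, preoperative mean | Flagged, 6 against 3 months |
|---|---|---|---|---|
| 0.5 | 0.113 | 0.505 | 13% | 5% |
| 0.7 | 0.088 | 0.652 | 16% | 5% |
| 0.9 | 0.051 | 1.130 | 30% | 5% |

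**4. Gradual fall of 2.5 SE by month 6.** With equal drops at each of the three visits, the last step is 2.5/3 = 0.833 and month 6 against month 3 flags Φ(0.833 − 1.65) = 21%. If the fall is linear in time, half of it lies between months 3 and 6, giving Φ(1.25 − 1.65) = 34%. Against the mean of two preoperative tests, either pattern gives Φ(2.887 − 1.65) = 89%.

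**5. Any-earlier-test reading, no true change.** With k earlier tests, P(flag) = ∫ φ(y)·[1 − Φ(y + 1.65√2)^k] dy.

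| k | 1 | 2 | 4 | 5 | 6 |
|---|---|---|---|---|---|
| Flagged | 4.9% | 8.7% | 14.3% | 16.5% | 18.4% |

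For month 6, k = 4 is the minimum; 5 and 6 correspond to three and four preoperative tests.

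**6. Each pair tabulated separately.** The 6-month against last-preoperative entry has a false-positive rate of 4.9%. Neither fault arises.

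**7. Fixed reference, flagged at any visit, no true change.** Against the mean of two preoperative tests, the share flagged at least once is 12.7% over months 1, 3 and 6, and 15.9% over all four visits.

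**The case against.** Preoperative tests are themselves preceding time points. A reader might infer that the plan rules out a preoperative comparison; the wording does not support that, because the comparison is included but not singled out. Pairwise tabulation would be sound, and nothing in the text says that a flag against any one earlier score is enough. This stands, and the point is therefore about an unfixed rule. It does not remove the difficulty, since the plan promises a count per segment and names no pairwise table.

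A reader might also infer that all three definitions exceed 5%. The inflation from a stated 5% concerns the RCI only. With r of 0.5 to 0.9, the 0.07 rule flags 33% to 16% of unchanged patients even with one fixed pair. The 20% rule (0.20 × 1.35 = 0.27) flags 4.6% down to 0.01% for one pair, and stays below 5% even against any of four tests when r is about 0.7 or higher.

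The 75%-against-5% contrast depends on a large fall. Two SEs of difference is 0.14 to 0.32 One-Back units over the same range of r, well above 0.07; step 3 gives the smaller contrast.

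Segment reporting is a legitimate description of when change occurs, and early decliners do appear in the first segment. Persistent average change is addressed by the interrupted time series model. All of this stands, and it limits the point to the individual classification.

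**Conclusion.** The point holds as a gap in specification with a real consequence. Followed segment by segment, the rule gives 3-, 6- and 12-month RCI percentages that flag a sustained early decline in only about 5% of patients whatever its size. Against the mean of two preoperative tests the figure is about 75% for a fall of 2 SEs of difference, or 13% to 30% for a fall of 0.07. If any earlier test counts, the false-positive rate at month 6 is about 14% at the minimum of four earlier tests and rises with the number of preoperative tests. The stated 5% belongs to a single pair. These sizes rest on independent normal errors of equal variance, and the 0.07 range rests on an assumed r.

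A reader might infer that the main result is compromised. It is not: the hypothesis on the mean 6-month score, the interrupted time series model and the sample size of 330 do not use this rule. The change is a cheap and worthwhile improvement.

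**What to change.** Replace the comparison sentence in section 3.6.1 with a rule along these lines: at each postoperative visit (1, 3, 6 and 12 months), decline is assessed once per patient against one prespecified preoperative reference, such as the mean of that patient's k preoperative tests. The RCI standard error should match that reference: for a single score minus a mean of k, σ·√(1 + 1/k) under the assumptions above.

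Report each visit's percentage separately, and do not attach the 5% to decline at any visit (step 7). Keep segment-to-segment change as a separate description, not labelled cognitive decline.

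This costs a few sentences and no new data. Two small downsides should be stated. The standard error must be scaled to each patient's number of preoperative tests. A flat preoperative mean also does not remove a preoperative trend, so attribution of decline to surgery stays with the interrupted time series model.
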